7.2.4 Pregnancy

Coversin (rVA576) is contraindicated during pregnancy. If pregnancy is suspected, a blood sample for serum HCG examination must be sent to the sub-contracted laboratory within 48 hours. As during the first pregnancy weeks the test may be negative it may be confirmed by an ultrasound examination. If at least one of the above-mentioned examinations is positive, administration of the IMP should be stopped and the patient must be immediately withdrawn from the study **unless** the patient consents to a termination in which case treatment would continue. All pregnancies (even if only suspected) must be reported on the appropriate eCRF page (and Pregnancy form to the Pharmacovigilance provider (PVP) of the Sponsor) within 24 hours from the moment when the investigator became aware of the pregnancy (or suspected pregnancy). In any case each pregnancy must be followed till its termination (either by birth of a child or abortion) and the eCRF page (and Pregnancy form) has to be updated. In the event of live birth, the child will be followed for 6 months.

Reporting to PVP of Sponsor shall be done on the corresponding Pregnancy form provided to each centre during the initiation visit, and sent by fax or e-mail to:

██

██

██ *Adverse Events*

Any signs or symptoms at an injection site following subcutaneous administration of the IMP are considered an Injection Site Reaction (ISR). An ISR is an AE and described in detail like an AE (e.g. onset date, relationship etc). The subcutaneous injection with the IMP is expected to produce localised events (e.g. mild pain/ mild erythema/ mild induration) over/around the injection site. These expected ISRs are listed in **Table 10**. The severity of an expected ISR is graded according to **Table 10**. The patient collects all ISRs in the diary card and only expected ISRs of grade 2 or higher are to be reported in the CRF by the investigator. Any other ISR (not listed in **Table 10**, i.e. blister/ulcer) of any grade will be reported in the CRF by the investigator.

Table 10: ISRs grading guidance

Local Reaction	Mild (Grade 1)	Moderate (Grade 2)	Severe (Grade 3)	Potentially Life Threatening (Grade 4)
Pain	Does not interfere with daily activity	Repeated use of non-narcotic pain reliever or interferes with daily activity	Any use of narcotic pain reliever or prevents daily activity	Accident & Emergency (A&E) visit or hospitalization
Tenderness	Mild discomfort to touch or does not interfere with daily activity	Discomfort with movement or limiting daily activity	Significant discomfort at rest or prevents daily activity	A&E visit or hospitalization
Itching	Does not interfere with activity	Limiting activities	Prevents daily activity	
Erythema/ Redness *	Erythema or redness ≤5 cm at the longest diameter	Erythema or redness: >5cm but ≤10cm at the longest diameter	Erythema or redness > 10cm at the longest diameter	A&E visit or hospitalization

Local Reaction	Mild (Grade 1)	Moderate (Grade 2)	Severe (Grade 3)	Potentially Life Threatening (Grade 4)
Induration/ Swelling	Soft swelling Induration ≤5 cm at the longest diameter	Soft swelling Induration: >5cm but ≤10 cm at the longest diameter	Soft swelling Or induration: > 10 cm at the longest diameter	Necrosis
Bruise/ hyperpigmentati on	Bruise /hyperpigmentation-≤5 cm at the longest diameter	Bruise /hyperpigmentation: >5cm but ≤10cm at the longest diameter	Bruise /hyperpigmentation: >10 cm at the longest diameter	Necrosis

AEs which appear to affect more than one patient, will be assessed for their severity, threat to the patient's health and drug relationship. Investigators may decide to withdraw their patients if continued study participation is not in the patient's best medical interest.

Only injection site reactions which are grade 2 or above will be reported.

All other adverse events, regardless of grade, will be reported.

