6.5 Interruption of Treatment

If treatment is interrupted, either for reasons outside the patient's or the investigator's control or because it is considered to be in the patient's best interest it may be resumed at the discretion of the investigator and Sponsor. Any interruption of >24 hours will require an ablating regimen of 60mg followed by 30mg 12 hours later before resuming normal dosing, this should be discussed with the Sponsor. In the event of an interruption of treatment of >28 days, the investigator should discuss with the Sponsor the advisability of resuming treatment.

7 Safety Reporting

All AEs occurring from the signing of the voluntary Informed Consent Form (ICF) to the end of the trial visit will be recorded. All adverse events, whether or not considered to be related to the study drug, will be monitored and reported at all stages of the study. Adverse events occurring between clinic visits will be reported by the patient or recorded at the next clinic visit and entered on the adverse event form of the case report forms. All adverse events must be fully recorded in the patient notes throughout the entire study period and will be transcribed into the subject's eCRF.

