7.2 Procedures for Recording of Adverse Events

7.2.1 General

All adverse events occurring during the Study (from the timepoint of signing of the Informed Consent Form (ICF) until completion of patient's study participation or premature withdrawal) observed by the Investigator or reported by the patient, whether or not attributed to the IMP, shall be recorded in patient's medical records and on the eCRF.

The following information shall be recorded:

- description,
- date of onset and end date,
- severity,
- assessment of relatedness to the IMP,
- seriousness,
- measures taken for management of the AE,
- outcome of the event.

Follow-up information should be provided as necessary.

AEs considered as being related to the IMP as judged by a medically qualified Investigator, or the Sponsor, must be followed until their resolution or when patient's status is considered as stable. All related AEs that result in a patient's withdrawal from the Study or are present at the end of the Study, should be re-evaluated and if needed followed until a satisfactory resolution occurs.

It will be left to the Investigator's clinical judgment whether or not an AE is of sufficient severity to require termination of IMP administration. A patient may also voluntarily withdraw from IMP administration due to AEs perceived as intolerable. If either of these occurs, the patient will be given appropriate care under medical supervision until symptoms cease or the condition becomes stable.

The severity of reported events shall be assessed on the following scale:

- 1 = mild
- 2 = moderate
- 3 = severe
- 4 = life threatening
- 5 = death

The causal relationship of AEs to the IMP must be assessed by the Investigator, or by a medically qualified designee, in accordance with the following criteria:

Term	Definition
Unrelated	Clinical event with an incompatible time relationship to administration of the investigational medicinal product (IMP), and that could be explained by underlying disease or other drugs or chemicals or is incontrovertibly not related to the IMP
Possibly related	Clinical event with a reasonable time relationship to IMP administration, and that is unlikely to be attributed to concurrent disease or other drugs or chemicals
Related	Clinical event with plausible time relationship to IMP administration and that cannot be explained by concurrent disease or other drugs or chemicals

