3.4.3 Adverse Events (AEs)

All AEs, which occurred at any time after signing the informed consent form (ICF), will be recorded in the electronic Case Report Form (eCRF). The following details will be reported for each adverse event:

- Start and stop dates
- Severity, using CTCAE grading 1 to 5
- Relationship to study treatment:
 - Unrelated
 - Possibly Related
 - Related
- Serious:
 - Yes
 - No
- Action taken with study treatment:
 - Dose increased
 - Dose not changed
 - Dose reduced
 - Drug interrupted
 - Drug withdrawn
 - Not applicable
 - Unknown
 - Other
- Outcome
 - Fatal
 - Not recovered/not resolved
 - Recovered/resolved
 - Recovered/resolved with sequelae
 - Recovering/resolving
 - Unknown

Other action taken, whether the AE caused discontinuation, details of death, hospitalisation, last dose before the event and other information related to the AE will be collected and listed.

Treatment emergent adverse events are defined as any AE with a recorded start date/time on or after the date/time of start of study medication. All patients enrolled into the CONSERVE study will have transitioned from a parent clinical trial and all will have been previously treated with rVA576, therefore all AEs recorded under protocol AK581 will be considered treatment-emergent.

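### Grade 1 injection site reactions not listed in Table 10 fall under two opposite reporting rules, and the SAP's AE tables do not say that expected grade 1 reactions are left out

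*Protocol*

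**What the plan says.** The ISR rules are in the protocol's section on reporting of adverse events (7.2.5 in the contents list), around Table 10.

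- **Status.** "An ISR is an AE and described in detail like an AE".
- **Before Table 10, expected reactions.** The patient notes all ISRs in the diary card, but "only expected ISRs of grade 2 or higher are to be reported in the CRF by the investigator".
- **Before Table 10, unlisted reactions.** An ISR that is not in Table 10, with blister or ulcer as the example, "of any grade will be reported in the CRF by the investigator".
- **After Table 10.** "Only injection site reactions which are grade 2 or above will be reported". The next sentence reads "All other adverse events, regardless of grade, will be reported".

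The general statements make no exception for ISRs.

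- **Opening of Protocol section 7.** "All AEs occurring from the signing of the voluntary Informed Consent Form (ICF) to the end of the trial visit will be recorded".
- **Protocol 7.2.1.** AEs observed or reported during the study, "whether or not attributed to the IMP, shall be recorded in patient's medical records and on the eCRF".
- **SAP 3.4.3.** "All AEs, which occurred at any time after signing the informed consent form (ICF), will be recorded in the electronic Case Report Form (eCRF".

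SAP 4.12.1 builds an overview (any AE, serious, drug-related, leading to death or discontinuation), a summary by MedDRA term and a summary by severity. These are Tables 14.3.1.1 to 14.3.1.4 in Appendix 1. The SAP mentions neither the grade 2 threshold nor ISRs as a category, and it plans no output from the diary ISR records.

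**The concern.** Adverse events are the first component of the primary endpoint (Protocol 3.2.1, SAP 2.4.1), and the product is self-injected every 12 or 24 hours. The protocol itself expects mild local pain, erythema and induration. Two things are at stake.

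First, a site holding a diary entry for a mild blister has one sentence telling it to enter the event and a later one telling it not to. Unlisted reactions are the ones the protocol does not count as expected, so they are the ones least suited to being dropped through an ambiguity.

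Second, someone working from the SAP alone would take the AE dataset to be complete from grade 1 upwards. The tables would then be read as the full AE burden, although one anticipated category, plausibly drug-related, had been left out by rule.

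**Working it through.** No arithmetic applies. The check sets each type and grade of ISR against the three rules.

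| ISR | Rule before Table 10 | Rule after Table 10 | All-AE statements (Protocol 7 and 7.2.1, SAP 3.4.3) |
|---|---|---|---|
| Expected (Table 10), grade 1 | diary only, not CRF | not reported | recorded |
| Not in Table 10, grade 1 | CRF | not reported | recorded |
| Any ISR, grade 2 or above | CRF | reported | recorded |

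**Row 2: direct contradiction.** The two ISR rules give opposite instructions. The later sentence is restrictive, and the one after it sends all *other* AEs to reporting at any grade. Read together, they divide ISRs from non-ISRs, which puts an unlisted ISR under the threshold. The visible text does not say which rule prevails. Table 10 gives grading criteria only for the reactions it lists, so a grade 2 cut-off for a blister would rest on the general five-point scale in 7.2.1.

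**Row 1: the ISR rules agree with each other.** Both keep expected grade 1 reactions off the CRF. They conflict only with the all-AE statements, which have no cross-reference to the exception.

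**Row 3: no conflict.**

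**Effect on the planned tables if sites follow the ISR section:**

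- *Any AE and drug-related AE (Table 14.3.1.1).* A patient is lost from a row only if the omitted reaction was the sole event qualifying for that row.
- *AEs by term (Table 14.3.1.2).* Each omitted reaction lowers the event count. A patient whose reactions of a given type were all grade 1 does not appear under that term.
- *Maximum severity (Table 14.3.1.3).* If the Table 10 grade is the severity carried into the dataset, the mild category for expected ISR terms is empty by construction.

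**Is the gap covered elsewhere in the SAP?** SAP 4.1 (changes from protocol) does not mention the threshold. Appendix 1 has no ISR table and no diary listing. Physical examination findings, which include injection site inspection, and the self-injection questionnaire are only listed (SAP 3.3.7 and 3.4.9). They do not replace AE counts.

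**Size.** This would need the proportion of patients whose only AE, or only drug-related AE, is an expected grade 1 ISR. The documents give no ISR rate of any kind, so the figure cannot be derived.

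**The case against.** The strongest reply is that this is a general rule followed by a stated exception. Section 7.2.1 is headed as general, and the ISR text later in 7.2 sets out the grade 2 threshold openly, twice. For expected reactions that reply is largely right. The protocol discloses its choice, and what is missing is a cross-reference. It does not rescue SAP 3.4.3, which repeats the all-AE statement and contains no exception anywhere.

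For unlisted reactions, one can argue that the earlier rule is the detailed, CRF-specific one and that the later line is a loose restatement. A site may well read it so. But the later line is unqualified and comes last, so the opposite reading is equally available.

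It is also fair that the information is not wholly lost. The diary holds all ISRs, injection sites are inspected at visits, and serious events are reported regardless. The analysis is descriptive and non-comparative, so no test or contrast between groups is affected.

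A reader might infer more than the documents support:

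- *That the two ISR rules conflict across the board.* They differ in one category only.
- *That the omission is concealed.* That is true of the SAP text and its planned tables, not of the protocol. Nor can it be said that the final report would leave readers unaware: table shells are in stand-alone documents (SAP section 6), and the report is to discuss methodology (Protocol 14.1).
- *That the bias can be sized from dosing frequency or patient numbers.* One or two injections a day is 365 to 730 a year (1 × 365, 2 × 365), and one patient in 50 is 2 percentage points (1/50). Neither says how often a mild ISR occurs or how many patients have no other AE. Even the 50 is only an approximate upper figure in the SAP.

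**Conclusion.** The point holds in two parts. The protocol contradicts itself on grade 1 ISRs outside Table 10, and a literal reading of its last rule would drop them from primary-endpoint data. Expected grade 1 ISRs are deliberately kept off the CRF, yet three passages say all AEs are recorded and the SAP's AE tables carry no caveat. The any-AE, drug-related and mild-severity counts therefore exclude those events by rule.

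The direction can only be towards fewer events; the size is unknown. This assumes that sites follow the ISR section. If some follow 7.2.1 instead and enter mild reactions, the tables would mix two capture rules. The documents do not show which rule sites used.

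This is an inexpensive reporting defect that should be corrected. It does not undermine the study, and it is no criticism of the decision to leave expected grade 1 reactions in the diary.

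**What to change.** 1. **Protocol, sentence after Table 10.** Bring it into line with the text before the table: the grade 2 threshold applies only to expected (Table 10) ISRs, and ISRs not listed there are reported at any grade.
2. **Protocol section 7, Protocol 7.2.1 and SAP 3.4.3.** State the exception, or cross-refer to it, wherever all AEs are said to be recorded.
3. **Site practice.** Confirm which rule sites applied. If some used the blanket threshold, unlisted grade 1 reactions would have to be recovered from the diaries, or their absence stated.
4. **Tables 14.3.1.1 to 14.3.1.3.** Once step 3 is done, add a footnote that expected grade 1 ISRs are excluded because they were not collected on the eCRF, worded to match what sites did.

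A separate ISR table is optional, since ISRs entered as AEs already appear by preferred term and severity.

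The cost is a few sentences in each document, three footnotes and a query to sites. The only extra data entry is any unlisted grade 1 reaction not already on the eCRF.

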7.3 Reporting Procedures for Serious Adverse Events

Any SAE occurring during the Study has to be managed by established Standards of Care to protect life and health of participating patients. If such treatment represents a significant deviation from the protocol, the Investigator shall immediately notify the study monitor and/or the Sponsor to determine whether the patient should be dropped out from the Study, or not.

All Serious Adverse Events, irrespective of their causality, must be notified to the Pharmacovigilance provider (PVP) of the Sponsor, **within 24 hours** of the Investigator becoming aware of the event. Reporting shall be done on the corresponding SAE form provided to each centre during the initiation visit, and sent by fax or e-mail to:

████████████████████
████████████████████

The information provided shall contain as much detail regarding the event as is actually available. Investigators should not wait to receive additional information to fully document the event, before notifying the SAE to Akari Therapeutics Plc. The SAE reporting form should detail all relevant aspects of the AEs listed in Section 7.2.1. Where applicable, information from relevant hospital records or autopsy reports should be obtained and provided to Akari Therapeutics Plc.

7.4 Expedited Safety Reporting

Any Serious Adverse Event, which is unexpected and at least possibly related to the IMP, requiring expedited reporting to the respective regulatory authority, EudraVigilance and ECs/ Institutional Review Boards (IRB) of the sites participating in this Study is subject to following timelines:

- 7 calendar days for SUSARs involving death and life-threatening events

- 15 calendar days for SUSARs involving hospitalization or prolongation of hospitalization or persistent or significant disability/incapacity or congenital anomaly/birth defect or any other significant clinical/laboratory event of major concern in the opinion of the Investigator.

Day zero (clock start) for expedited reporting purposes is the date of initial information or of the relevant follow-up information received in any form (in writing or verbally) by any personnel of the Sponsor or contracted parties including the CRO and the PVP.

All SUSARs will be reported to the respective competent authorities, ECs (IRBs) and Investigators within specified timelines in accordance with corresponding national legislation.

7.5 Development Safety Update Reports

Development Safety Update Reports will be prepared by Akari Therapeutics Plc (or designee), on an annual basis and distributed to all competent authorities and to relevant ECs in accordance with the corresponding national regulations.

8 Data Handling and Source Documents

Patient data will be collected on eCRFs and will be substantiated by source documents at the clinical site. The eCRFs will be completed according to guidelines provided by the CRO and their SOPs. Source documentation supporting the eCRF data should indicate the patient's participation in the study and should document the dates and details of all study procedures, AEs and patient status.

The Investigator must maintain source documents, such as laboratory reports, complete medical history, ECG read outs and physical examination reports. All source documents should be accessible for verification by the site monitor, auditor, the EC, or for inspections by the regulatory authorities. In addition, the site will allow the Sponsor and assigned CRO direct access to all source documents and will permit trial-related auditing of clinical, pharmacy and laboratory facilities.

Direct access to these documents must be guaranteed by the Investigator or their designee, or the study coordinator, who must provide support at all times for these activities.

The nature and location of all sources of original data required to complete the eCRF will be identified by the CRO and the site staff.

Parent trial data used to assess patient safety and eligibility for enrollment will be entered into the AK581 database. Where applicable, assessment data collected at the subject's parent trial end of study visit will be captured. Coversin dosing history, parent trial ECG and LDH results, and plasma (blood) transfusion/dialysis history will be available in the AK581 subject casebooks.

The Study Monitor will perform 100% source data verification to ensure adequate quality control and assurance of patient data. An explanation of missing data must be given.

All data entered into the eCRF will be saved directly into the study database. This data will be validated both manually and programmatically. Clarification of data will be requested from the study site as requested. The database will be quality assured and will be available for statistical analysis according to the SAP.

Patient data will be reviewed for major protocol deviations by the Study Monitor during site visits and the entire team will review the database at timed intervals prior to the database lock.

9 Statistics

9.1 Statistical methods

A Statistical Analysis Plan (SAP) is in place. There will be no formal statistical inferences. All the study data will be analysed descriptively. Standard summary statistics will be produced for observed values, and changes from entry (where applicable) at the relevant post-entry timepoint.

For continuous variables, these statistics will include the number of patients with available data, mean, standard deviation, median, minimum, maximum. For categorical variables, these statistics will consist of patient counts and associated percentages. Unless otherwise specified, missing data will not be included in the denominator for percentage calculation. Time to event data will be summarised using graphs and summary statistics from the Kaplan-Meier method.

Listings will also be used to display data at the individual patient's level.

Data will be reported at each 3-month time point since the start of the study (where applicable) and over the entire period of the study (where applicable).

Results will be reported for all patients and then separately for PNH and aHUS patients.

- The incidence of AEs, and serious adverse events (SAEs) will be summarised over time for all patients.
- Vital signs, results of standard laboratory tests (clinical chemistry, haematology and urinalysis), and results of limb lead or 12 lead electrocardiograms (ECGs) will be summarised over time for all patients.
- The proportion of subjects with no adverse change in overall scores of Quality of Life using the EORTC QLQ-C30 (some PNH patients only), the EQ-5D-5L and FACIT-F instruments will be summarised over-time.

For PNH patients, additional summaries will include :

- The proportion of subjects with thrombotic and haemolytic event-free status
- The time to thrombotic or haemolytic event since entry.
- The time to first transfusion since entry.
- The proportion of subjects with serum Lactate Dehydrogenase (LDH) <1.8, >1.8 to 2.4, >2.4 to 3, and >3 times the upper limit of normal (ULN).

- The proportion of subjects with median serum Lactate Dehydrogenase (LDH) <1.8, >1.8 to 2.4, >2.4 to 3, and >3 times the upper limit of normal (ULN).
- The proportion of subjects who require PRBC transfusion.
- The proportion of transfusion independent subjects, with haemoglobin (g/L) above the baseline haemoglobin value they had at the start of the parent trial.
- The proportion of transfusion-independent subjects over the entire duration of the study with mean haemoglobin (g/L) above the baseline haemoglobin value they had at the start of the parent trial.
- The incidence, number and time to first Major Adverse Vascular Event (MAVE) for each PNH subject will be summarised.

Results may also be reported separately for i) subjects who were transfusion-dependent when they started receiving rVA576 (Coversin), and ii) subjects who were transfusion-independent when they started receiving rVA576 (Coversin), and further stratification of these proportions by a) patients who were complement inhibitor naïve prior to treatment with rVA576 (Coversin), and b) patients who received treatment with another complement inhibitor before switching to rVA576 (Coversin) and where applicable i) transfusion-independent prior to receiving rVA576 (Coversin) and remain transfusion-independent and ii) transfusion-dependent prior to receiving rVA576.

For aHUS patients, additional summaries will include:

- The proportion of subjects with Normal Platelet count [defined as Platelet count $\geq 150 \times 10^9/L$]
- The proportion of subjects entering the study with complete TMA response who continue to exhibit complete TMA response with preserved renal function, defined as haematologic normalization (platelet count $\geq 150 \times 10^9/L$ and $LDH \leq ULN$) and preservation of kidney function (<25% increase in SCr from baseline of the parent trial).
- The proportion of subjects with complete TMA response with improved renal function defined as normalization of haematological parameters (normalisation of platelet count and $LDH \leq ULN$) and $\geq 25\%$ decrease in SCr from baseline of the parent trial.
- The proportion of subjects who exhibit haematological normalisation (platelet count $\geq 150 \times 10^9/L$ and $LDH \leq ULN$).

The proportion of subjects with improvement in renal function defined as a decrease in SCr over three consecutive measurements from baseline of the parent trial without the need for dialysis even if not within the normal range.

- The proportion of subjects who are TMA event-free.
- Platelet mean count change over-time.

Other endpoints will be described as indicated above depending on whether its outcome measure is a continuous or categorical variable.

